### 6.3.2 Entinostat-related Hematologic Toxicity

The guidelines in Table 6-2 will be followed for determining the timing of cycles based on hematologic status at the time of planned dosing.

**Table 6-2 Hematologic Toxicity: Dose Modification for Entinostat**

Toxicity	Dose modifications 
≥Grade 3 neutropenia, ≥Grade 3 uncomplicated thrombocytopenia, or Grade 2 complicated thrombocytopenia	
Administer symptomatic remedies/ start prophylaxis.
 
Hold dose until recovery to Grade 1 or study baseline.
 
 
If not recovered by next scheduled dose, skip the dose. If recovered by next scheduled dose, resume study drug at prior dose.
 
If receiving 2 mg dose, and not recovered by either of the next 2 scheduled doses, permanently discontinue study treatment. Otherwise, skip each dose. If recovered for either of these doses, resume study drug as follows: 
 
If receiving 5 mg, restart study drug at 3 mg.
 
If receiving 3 mg, restart study drug at 2 mg.
 
 
 
If dose is held for 4 consecutive weeks, permanently discontinue study drug.
 

Recurrence of the same hematologic toxicity	
If the same hematologic toxicity recurs:
 
 
Administer symptomatic remedies/ start prophylaxis. If receiving 2 mg, permanently discontinue study drug. Otherwise, hold dose until recovery to Grade 1 or baseline.
 
If receiving 2 mg dose, and not recovered by either of the next 2 scheduled doses, permanently discontinue study treatment. If recovered for either of the next 2 scheduled doses, resume study drug as follows: 
 
If receiving 5 mg, restart study drug at 3 mg
 
If receiving 3 mg, restart study drug at 2 mg
 
 
 
If the same ≥Grade 3 event recurs (i.e., third occurrence) despite entinostat dose reduction to 2 mg, as described above, discontinue study drug.
 

 If Entinostat dose is reduced, an increase in dose to prior level can occur only after the AE has completely resolved.

 If greater than 50% of doses are missed during any 6 week period, discontinue from study drug treatment.

**Please note:** Patients that do not require a dose reduction due to AE during the first treatment cycle should continue at 5mg weekly for at least one more cycle prior to changing to 10mg biweekly.

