Entinostat has also been shown to modify the phenotype of cancer cells from a mesenchymal to an epithelial one, with impact on reducing the metastatic potential of the cancer cells ([Shah 2014](#)). In addition, there is a suggestion that entinostat may have longer term effects on cancer phenotypes, cancer stem cells (CSCs) or progenitor cell pool and potential sensitization to subsequent post-study treatments ([Juergens 2011](#)).

Most recently, entinostat has been shown to down-regulate the number and function of two key immunosuppressive cells, myeloid derived suppressor cells (MDSCs) and regulatory T-cells (Tregs), in the tumor microenvironment thereby enhancing the activity of immune checkpoint inhibition.

To date, entinostat has been investigated alone or in combination in >900 patients with cancer in clinical studies, including >600 patients with solid tumors. Entinostat as a single agent has been studied in metastatic melanoma and in combination has been studied in metastatic NSCLC, breast cancer, renal cell cancer, and colon cancer. Evidence of the efficacy of entinostat was seen in patients with nonresectable Stage IV melanoma, with 25% of patients experiencing disease stabilization ([Hauschild 2008](#)). Based on these encouraging findings, further investigation of entinostat in combination was considered warranted in patients with melanoma. In combination studies, clinical activity of entinostat combined with exemestane was demonstrated in ER+ post-menopausal women with advanced breast cancer enrolled in the ENCORE 301 study. Prolonged PFS and OS were observed, resulting in a breakthrough therapy designation for entinostat. A phase III study has been initiated based on the results of ENCORE 301 and is currently enrolling patients.

Overall, among all patients treated, entinostat has been well tolerated at the doses and schedules investigated. Regardless of indication and regimen, the most frequently reported adverse events (AEs) with entinostat included gastrointestinal (GI) disturbances, primarily nausea with or without vomiting and diarrhea; fatigue; and hematologic abnormalities, primarily anemia, thrombocytopenia, neutropenia, and leukopenia. Most occurrences of these events are Grade 1 or 2 in severity and non-serious. Grade 3 and 4 hematologic abnormalities are commonly seen in patients with hematologic malignancies, but are much less prevalent in patients with solid tumors.

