### **6.1 Entinostat Administration**

The starting dose of entinostat will be 5 mg administered orally every week (days 1, 8, 15, and 22) of a 28 day treatment cycle. The dose may be changed from 5 mg weekly to 10 mg every two weeks after cycle 1 for patients who have not experienced treatment-related adverse events (excluding manageable events) with severity grade  $\geq 2$  (moderate). Provisions for dose reductions are described in Section 6.3.

Entinostat is supplied in 5 mg (intense yellow in color) and 1 mg (light brown in color) coated tablets. Study drug should be taken in the morning. Tablets should be taken on an empty stomach, at least 2 hours after a meal and at least 1 hour before the next meal.

Tablets should be taken whole and not crushed. If a patient vomits after taking a dose of medication, dosing should not be re-administered but instead the dose should be skipped. If the patient inadvertently missed the dose on scheduled day, the dose could be taken within 2 days of the scheduled dose. However, all efforts should be made to adhere to dosing schedule.

Procedures for dose reductions and delays due to toxicity are summarized in Section 6.3. In the event of necessary dose reductions, each study site pharmacy will be supplied with 1.0 mg tablets in addition to the 5.0 mg tablets.

Unused tablets or empty bottles will be returned to the clinic for accountability purposes.

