## **6.2 Treatment Duration**

Patients who display progressive disease or unacceptable toxicity to treatment will be removed from protocol treatment at the time that event is documented. Further disease management will be at the investigator's discretion. If the patient withdraws from study treatment due to toxicity related to study drug, the patient will be followed until the resolution or conclusion of the event.

All patients will be treated until progression or intolerable toxicities occur.

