## **6.3 Dose Adjustments**

**Adverse events** that are classified as unrelated or unlikely related do not require dose adjustment, and the prior dose can be resumed once the **adverse event** has resolved. For toxicities that are classified as possibly related to the AE, dose adjustment should be addressed as follows:

For patients who are escalated to 10 mg every two weeks, any toxicity  $\geq$  Grade 2 will result in an initial reduction to 5 mg every two weeks. If the grade of the toxicity is  $\leq$  grade 2 for all toxicities or  $\leq$  grade 3 for laboratory abnormalities other than hepatic, renal or hematologic, an increase in dose to the prior level can then occur after the toxicity has completely resolved and the 5 mg every two weeks dose has been shown to be tolerable. Patient may then receive either 10 mg every two weeks or 5 mg every week at the discretion of the investigator.

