### **6.3.1 Entinostat-Related Non Hematologic Toxicity**

The rules outlined in Table 6-1 are to be followed for the management of non-hematologic toxicities that are probably or definitely due to entinostat, with toxicities graded by the Investigator according to the NCI, CTCAE, version 4.03.

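### The hematologic dose-hold trigger in Table 6-2 omits complicated thrombocytopenia of grade 3 or 4, probably through a dropped ≥ sign

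*Combined protocol and SAP*

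**What the plan says.** Section 6.3.2 sends sites to Table 6-2 for dosing decisions "based on hematologic status at the time of planned dosing". The first row of that table is triggered by "≥Grade 3 neutropenia, ≥Grade 3 uncomplicated thrombocytopenia, or Grade 2 complicated thrombocytopenia". Once triggered, the row does three things:

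- It holds drug until the toxicity returns to grade 1 or to baseline.
- It sets the restart dose. The prior dose is resumed if the patient has recovered by the next scheduled dose. Otherwise the dose steps down from 5 to 3 mg or from 3 to 2 mg.
- It stops drug permanently after a hold of four consecutive weeks.

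A second row deals with recurrence of the same hematologic toxicity and states no grade.

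Three other places could bear on a platelet event:

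- Section 6.3.1 confines Table 6-1 to the "management of non-hematologic toxicities that are probably or definitely due to entinostat".
- Section 6.3 has a general reduction, which opens "For patients who are escalated to 10 mg every two weeks, any toxicity" and acts from grade 2 upward.
- Section 6.2 says that patients with "unacceptable toxicity to treatment will be removed from protocol treatment at the time that event is documented". It gives no grade.

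On regimen, Section 6.1 states: "The starting dose of entinostat will be 5 mg administered orally every week".

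**The concern.** The pattern of the trigger is easy to see: a complication lowers the hold threshold from grade 3 to grade 2. A threshold of that kind has to be open at the top, and the first two items are. The third is not. As printed, the rule holds drug for the mildest complicated event in the range and omits the more serious ones, which cannot be a deliberate choice.

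What is at stake is the safety of individual patients and consistent handling across up to four centers. An investigator faced with a first grade 3 or 4 complicated event would very likely hold drug. But the recovery threshold, the restart dose and the four-week stop all belong to a row that the event does not literally enter. Sites would have to improvise these, and a monitor checking treatment compliance would have no text to check against. Section 11.4 specifies no formal safety stopping rules, so the per-patient dosing rules carry more of the weight.

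**Working it through.** No sample size, power or error-rate figure bears on this point. The check is a cross-tabulation of the printed trigger, followed by a search for any other rule that fills the empty cells.

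**Step 1. The trigger, cell by cell.** Grade 3 or higher is taken as grades 3 and 4.

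| Thrombocytopenia | Grade 2 | Grade 3 | Grade 4 |
|---|---|---|---|
| Uncomplicated | not a trigger | held | held |
| Complicated | held | not named | not named |

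Grade 2 uncomplicated is left out of the count, because nothing in the protocol suggests that it should trigger a hold. That leaves 2 uncomplicated + 3 complicated = 5 cells. The printed text names 2 + 1 = 3 of them and omits 5 − 3 = 2.

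**Step 2. Other rules for the two empty cells, for a patient on weekly dosing.**

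| Place | Why it does not supply the rule |
|---|---|
| Table 6-1 (Section 6.3.1) | Non-hematologic toxicity only. It may catch the bleed, but not the platelet event. |
| Section 6.3, general reduction | Only for patients moved to 10 mg every two weeks. |
| Section 6.2 | Removal for unacceptable toxicity, with no grade, hold or restart dose. |
| Section 7.2 | Blood results must be reviewed before the next dose, but no action level is set. |

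**Step 3. Partial cover that does exist.**

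- The recurrence row of Table 6-2 has no grade limit. A patient with an earlier listed event whose toxicity recurs at grade 3 or 4 complicated is arguably covered.
- A hold begun at grade 2 complicated lasts until grade 1 or baseline, so worsening during that hold is covered.
- If the bleed is itself graded 3 or 4 and judged probably or definitely due to entinostat, Table 6-1 holds drug.

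What remains uncovered is chiefly a first event detected at grade 3 or 4 complicated.

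**Step 4. Who is exposed, and for how long.** Everyone starts on weekly dosing. Section 6.1 allows a change after cycle 1: 1 cycle × 4 doses = 4 weekly doses. The note under Table 6-2 says that patients who needed no reduction in the first cycle "should continue at 5mg weekly for at least one more cycle prior to changing to 10mg biweekly": 2 cycles × 4 doses = 8 weekly doses. Patients who stay on weekly dosing remain exposed throughout treatment.

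**Step 5. After the correction.** If the last item reads grade 2 or higher, complicated grades 2, 3 and 4 are all named, and 5 of 5 cells are covered.

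**The case against.** The best reply is that this is a typing slip that no competent investigator would be misled by. The intent is plain from the rest of the row, and the authors are loose with the sign elsewhere: the recurrence label in Table 6-1 says grade 3, while the rule beside it says grade 3 or higher. Section 6.3.2 calls the table guidelines, whereas Section 6.3.1 speaks of rules. Section 6 leaves treatment responsibility with the investigator, and Section 7.2 requires results to be reviewed before dosing. Section 2.2 reports that grade 3 and 4 hematologic abnormalities are common in hematologic malignancies "but are much less prevalent in patients with solid tumors". At most 40 patients will be enrolled.

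Most of this stands. It is a slip, the gap is narrow and events should be few. It does not remove the point. Guidelines that the protocol says will be followed are still the operative dosing text, and an inferred hold does not tell a site when to restart, at what dose, or when to stop for good. A sign lost in file conversion cannot be wholly excluded, but the two other signs in the same cell are intact.

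A reader might go further and infer that patients with severe complicated thrombocytopenia have no protection at all. The partial cover in Step 3 and the removal clause in Section 6.2 rule that out.

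A reader might also see faults in the recurrence rows. For a patient at 2 mg, items 1 and 2 of the recurrence row in Table 6-2 differ on when drug stops. Neither gives a 2 mg restart dose, so only the timing differs and no further drug is authorised either way. The recurrence rows of both tables also give no restart dose for recovery later than the next two scheduled doses. Drug then simply stays held, and a tighter restart window after a second event may be deliberate caution. Loosening it would be a clinical preference that the documents do not support.

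**Conclusion.** The point holds in a limited form. As printed, Table 6-2 leaves out 2 of the 5 thrombocytopenia categories that should trigger a hold. For a weekly-dosed patient whose first event is found at grade 3 or 4 complicated, the protocol gives no hold, restart or stopping rule. All patients are potentially exposed for at least their first 4 weekly doses. The documents give no event rate, so the expected number of affected patients cannot be stated beyond saying that it should be low.

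This rests on reading the trigger literally and on taking the missing sign as absent from the sponsor's own copy. If that copy carries the sign, the point falls away. Nothing here touches the two-stage design, its error rates or the primary response analysis, and it would be wrong to infer any such effect. It is a safety-table correction that should be made, but it does not block the trial.

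**What to change.** In the first row of Table 6-2, change the last trigger item to *≥Grade 2 complicated thrombocytopenia* and leave the other two items as they are. The existing hold, restart and four-week stop then apply to every complicated grade from 2 upward.

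The protocol does not say what makes thrombocytopenia complicated. A short definition could usefully go in at the same time, although the correction does not depend on it.

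The cost is one symbol in a protocol amendment, which can travel with the next one submitted for IRB approval. It needs no new visits, procedures or patients. The recurrence rows need no change on this account.

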## 6.4 Concomitant Therapy

Throughout the study, investigators may prescribe any concomitant medications or treatments deemed necessary to provide adequate supportive and palliative care with the exception of those listed in Section 6.5. Please note: Patients on somatostatin analogues for symptom control may continue to receive them for symptom control.

## 6.5 Prohibited Medication

The following medications are prohibited:

- Valproic acid, Zolinza™ (vorinostat), Istodax® (romidepsin) or any other HDAC inhibitor
- DNA methyltransferase inhibitors (such as azacytidine (Vidaza®), decitabine (Dacogen®), and any experimental DNA methyltransferase inhibitor compounds),
- Other anticancer treatment including, but not limited to chemotherapy and radiotherapy.
- Corticosteroids. Topical steroids, such as nasal sprays, inhalers, ointments, are allowed. Systemic glucocorticoids are allowed for emergent medical conditions such as seasonal allergies and exacerbation of COPD for up to 2 continuous weeks; the medical monitor must be notified if such drugs are initiated for emergent conditions and be consulted should prolonged treatment be required. In patients with severe nausea or vomiting refractory to available anti-emetic therapies other than corticosteroid, a single dose of dexamethasone up to 10 mg (or equivalent), as part of antiemetic regimen to treat or prevent emesis is allowed. Patients should not have received corticosteroids for treatment of any disease within 2 weeks of Cycle 1 Day 1.
- Other investigational therapy
- Radiation therapy  
*Note: Radiation therapy to a symptomatic solitary lesion or to the brain may be considered on an exceptional case-by-case basis after consultation with sponsor. The patient must have clear measurable disease outside the radiated field. Administration of palliative radiation therapy will be considered clinical progression.*
- Traditional herbal medicines; these therapies are not fully studied and their use may result in unanticipated drug-drug interactions that may cause or confound the assessment of toxicity

## 6.6 Medications to Avoid

The following types of medications should be avoided if possible:

- Gastric acid reducing drugs (e.g. proton pump inhibitors [PPI], histamine receptor antagonists [H2], antacids; see Appendix 3)
- Sensitive substrates of CYP1A2, CYP2C6, and CYP2B8 (see Appendix 3)
- Drugs that are known to inhibit or induce P-gp (see Appendix 3)

## 7. STUDY TESTS AND OBSERVATIONS

Protocol-required tests, observations, and procedures are summarized in the Schedule of Study Assessments. Each cycle consists of 28 days. Patients will self-administer entinostat as described in Section 6.1. During cycle 1, patients will be required to visit the clinic on Days 1, 8, and 15. For all other cycles, patients will be required to visit the clinic on Day 1 and 15 only.

### 7.1 Screening

Screening tests are to be performed within 14 days prior to Cycle 1 Day 1 (C1D1) except as otherwise indicated.

- Informed Consent
- Medical history, including current medications taken within the past 28 days
- Physical examination
- Vital signs and weight
- ECOG performance score
- 12-lead ECG (within 14 days prior to C1D1)
- Coagulation tests (PT, PTT)
- Serum pregnancy test for women of child bearing potential only
- Hematology (CBC with differential, PLT, RBC, HGB, HCT)
- Blood chemistries [ALT, AST, alkaline phosphatase, albumin, total bilirubin, BUN, calcium, creatinine, electrolytes (sodium, potassium, magnesium, chloride, bicarbonate), glucose, LDH, phosphorus, total protein], uric acid.
- Urinalysis
- Contrast CT **and** octreotide scan for disease assessment (if one has not been performed within 28 days prior to C1 D1). The same method used at baseline should be used for all serial measurements.

- Clinical disease assessment for palpable or visual lesions
- Assessment of baseline signs and symptoms (adverse events will be collected starting at the time the patient signs the informed consent form and will be listed as pre-treatment emergent)
- Access to archival pathology tissue is required for molecular analysis. If archival tissue is not available for molecular analysis, tumor biopsy may be requested if there is a metastatic site easily accessible for needle biopsy.
- Concomitant medications taken within 28 days of cycle 1 day 1

## **7.2 Day 1 Visit Assessments (All cycles)**

Patients will make clinic visits for tests and observations according to the schedule in Schedule of Study Assessments (Appendix 1). Assessments may be performed up to 2 days and CT/ scans may be performed up to 7 days prior to the scheduled study visit day. The results of study blood tests must be available and reviewed by study site staff for toxicity and adverse events before the next dose of entinostat is administered. Obtaining blood for these tests may be performed locally or drawn by a home health care worker if clinic visits are not practical. Results must be sent to the investigator. Other observations should be performed prior to the next dose of entinostat.

Required procedures are as follows:

- Concomitant medications
- Adverse Events
- Hematology (as at screening)
- Blood chemistries (as at screening with the exception of magnesium which does not need to be done unless clinically indicated)
- Symptom directed PE (capture B symptoms)
- Vital signs and weight
- ECOG performance score
- Clinical disease assessment for palpable or visual lesions
- CT scan for disease assessment (up to 7 days prior to day 1 of odd cycles beginning with Cycle 3). In patients completing >9 cycles, scans are required every 3-4 months and/or omitting the use of contrast dye to every other restaging. Follow-up scans should include

the area of interest, the prospectively selected indicator lesion(s); the same method used at baseline should be used for all serial measurements.

- Entinostat compliance assessment

### **7.3 Day 8, 15, 22 Visit Assessments**

See Appendix 1 for full details on required visit assessments for Day 8, 15, and 22 visits according to cycle number.

### **7.4 End of Treatment Visit Assessments**

This visit should occur within one week from the date that the physician decides to discontinue study treatment. If the physician decides to discontinue study treatment due to disease progression, this visit should be completed before beginning the patient on another therapy.

Required procedures are as follows:

- Physical examination
- Vital signs and weight
- ECOG performance score
- ECG (as at screening)
- Concomitant medications
- Adverse events
- Hematology (as at screening )
- Blood chemistries (as at screening with the exception of magnesium which does not need to be done unless clinically indicated)
- Contrast CT scans for disease assessment if progression has not been observed previously. Follow-up scans should include the area of interest, the prospectively selected indicator lesion(s); the same method used at baseline should be used for all serial measurements. Octreotide scans should be done if any mass detected by CT completely resolves during treatment.
- Compliance assessment
- Clinical disease assessment for palpable or visual lesions

## **7.5 Safety Follow-up Visit**

Patients terminating study drug will return to the clinic within 30 days following the End of Treatment visit for the following procedures.

- Physical examination
- Vital signs and weight
- ECOG performance score
- 12 lead ECG (if new abnormality is observed during study and not resolved at EOT)
- Concomitant medications
- Adverse events
- Hematology (if new abnormality is observed during study and not resolved at EOT)
- Blood chemistry (if new abnormality is observed during study and not resolved at EOT)
- Any other tests required for appropriate follow-up given the nature of the toxicity

